7 ANALYSIS POPULATIONS

7.1 Screened Population

The Screened population consists of all subjects who have signed the informed consent.

7.2 Intent-to-Treat Population (ITT)

The intent-to-treat (ITT) population consists of all subjects who received study drug.

Receiving study drug is considered to have taken at least 1 full dose (80 mg Debio 1347) of study drug. Subjects will be analyzed according to their assigned cohort.

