## 11.3. Analysis Population

### Intent-To-Treat Population

The intent-to-treat (ITT) population consists of all subjects who received study drug.

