### Safety Population

The safety population consists of all subjects who received study drug.

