#### 11.5.6. Efficacy

The ITT population will be the primary analysis population for efficacy analysis. Efficacy analyses will be repeated on the mITT population and the PP population as supportive analyses. The efficacy analysis will be conducted using centrally measured response as primary analysis and repeated on locally measured response as sensitivity analysis.

**Best overall response** is defined as the best confirmed response observed from first administration of study drug until disease progression. A PR or CR response needs to be confirmed in the following assessment performed at least 4 weeks later. For subjects who experience clinical progression, a radiological assessment will be performed to confirm the progression and the results of radiological assessment will be used in the efficacy derivation.

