1 INTRODUCTION

This statistical analysis plan (SAP) describes the statistical analyses planned to be performed for the study Debio 1347-201 entitled “A Phase II basket study of the oral selective pan-FGFR inhibitor Debio 1347 in subjects with solid tumors harboring a fusion of FGFR1, FGFR2 or FGFR3”. The SAP is compliant with the study protocol version 3, dated of July 16th 2020. The SAP will be finalized prior to the database lock for the main analysis.

The rationale for Protocol Amendment 2 (PA2) was

- The results of data monitoring reviews of pooled data (Section **Error! Reference source not found.**) showed that the antitumor activity of Debio 1347 was lower than initially assumed at the time the protocol was developed. Considering that further enrolment is unlikely to substantially change the magnitude of the efficacy observed up to now, Debiopharm decided to permanently halt the enrolment in the study after consultation with the IDMC on June 10th, 2020.

After implementation of PA2:

- After consenting to PA2, on-treatment subjects will no longer be assessed for efficacy in the study, but only for safety.
- Off-treatment subjects will not be followed for disease status or survival in the study, but only for safety up to 30 days post last dose of Debio 1347.
- Subjects will complete study participation at 30 days after the last dose of Debio 1347. In the case of off-treatment subjects with >30 days and <2 years follow-up at the time of PA2 implementation, then these subjects can complete study participation immediately.

The SAP will pre-specify the statistical consideration for the analysis of study data to ensure validity of study findings and conclusions regarding study objectives.

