3.1 Primary Endpoint

The primary endpoint is ORR, defined as the proportion of subjects with a best overall response (BOR) of partial or complete response as centrally measured by RECIST 1.1 criteria.)

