7.5 Safety Population (SAF)

The Safety population consists of all subjects who received study drug.

Receiving study drug is considered to have taken at least 1 full dose or partial dose of study drug.

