10.2 Efficacy Analyses

The efficacy analysis will be performed on the ITT population as the primary analysis. All efficacy analyses will be repeated on the mITT and PP population as supportive analysis, unless otherwise stated.

PA2 shortens the data collection period for efficacy data. Compared to early enrolled subjects, the later enrolled subjects will systematically have less tumor response assessments at PA2 implementation and time to event variables censored at date of last dose. There will be no additional statistical considerations to specifically address these systematic differences between earlier and later enrolled patients, and therefore, the planned statistical methods remain same as before PA2 was implemented.

Also, since the homogeneity assessment at interim analysis was not conducted, the efficacy endpoints will be analyzed and reported by cohort and pooled total subjects.

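### SAP 7.2 limits the ITT population to subjects who took a full 80 mg dose, whereas the protocol includes everyone who received study drug; the likely effect on ORR is very small

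*SAP*

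**What the plan says.** Protocol 11.3 gives the ITT and Safety populations the same definition. For ITT: "The intent-to-treat (ITT) population consists of all subjects who received study drug". For Safety: "The safety population consists of all subjects who received study drug". Neither carries a dose threshold, so under the protocol they are the same set of people.

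The SAP repeats the protocol's ITT sentence in section 7.2 and then adds an operational rule: "Receiving study drug is considered to have taken at least 1 full dose (80 mg Debio 1347) of study drug". For the Safety population, section 7.5 interprets the same phrase differently: "Receiving study drug is considered to have taken at least 1 full dose or partial dose of study drug".

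ITT is the primary efficacy set in both documents. Protocol 11.5.6: "The ITT population will be the primary analysis population for efficacy analysis". SAP 10.2: "The efficacy analysis will be performed on the ITT population as the primary analysis". SAP 7.3 and 7.4 build mITT and PP as subsets of ITT. The SAP introduction says: "The SAP is compliant with the study protocol version 3". The modification history in SAP 11 does not mention a change to the ITT definition, although its entry for version 2.0 is very short.

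**The concern.** One phrase has two meanings within SAP section 7, and only the Safety meaning agrees with the protocol. Tablets are 20 mg (Protocol 7.1), so an 80 mg dose is four tablets and a partial intake is possible. Someone who took fewer than four tablets and never completed a full dose has been treated and counts for safety, but is absent from all three efficacy populations. No planned efficacy analysis brings that subject back, and Protocol 6.3 allows no replacement.

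SAP 3.1 gives ORR as a per-subject rate: "defined as the proportion of subjects with a best overall response (BOR) of partial or complete response as centrally measured by RECIST 1.1 criteria". The size of ITT is therefore its denominator. SAP 10.2.1 otherwise takes the conservative course: a subject with no radiologic assessment is classed as NE and stays in the denominator as a non-responder. A subject who never managed a full dose would most likely fall in that group, and the threshold removes that subject before the NE rule applies. Low exposure is already dealt with in the PP set, through the 75% cumulative-dose criterion in SAP 7.4, and the SAP gives no reason for a second exposure filter in ITT.

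At stake are conformity of the primary analysis set with the protocol and a probable small upward shift in ORR.

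**Working it through.** **Step 1. Who falls between the definitions.**

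| Subject | Protocol ITT | Protocol Safety | SAP ITT | SAP Safety |
|---|---|---|---|---|
| Took at least one full 80 mg dose | in | in | in | in |
| Took only partial doses | in | in | **out** | in |
| Took nothing | out | out | out | out |

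The only disagreement is in the second row. Because mITT and PP are subsets of ITT, that subject leaves them too.

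**Step 2. How many.** The documents give no count. Protocol 5.2 starts every subject at 80 mg once daily, and the reductions in Protocol 5.3.1 come after that start, so a dose-reduced subject would normally have taken a full dose already. Assumption: zero to two subjects.

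**Step 3. The base for an illustration.** The only response counts in the documents are those of the second IDMC review in SAP Table 6. The primary endpoint is centrally read and confirmed, so the central row is the closer one, although it counts unconfirmed responses. Reproducing it: 3/63 = 4.76%, printed as 4.8%; cohort 1, 2/30 = 6.67%, printed as 6.7%.

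SAP 9.3 calls these 63 subjects evaluable. SAP 10.8.1 defines evaluable, for the planned interim analysis, as ITT members with a post-baseline assessment or progression. If that definition carried over to the second review (an assumption), the 63 are already inside the SAP's ITT. Partial-dose-only subjects would then have to be added to 63, not subtracted from it.

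**Step 4. Effect of restoring the protocol definition,** with k added subjects, all non-responders: ORR = 3/(63 + k).

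- k = 0: 3/63 = 4.76%
- k = 1: 3/64 = 4.69%
- k = 2: 3/65 = 4.62%

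The pooled change is at most 4.76 − 4.62 = 0.14 percentage points. If both subjects belonged to cohort 1, its rate would go from 2/30 = 6.67% to 2/32 = 6.25%, a change of 0.42 points.

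**Step 5. Comparison with 15%.** The one-sided exact p-value, P(X ≥ 3) with n = 63 and a true rate of 0.15, is 0.997. With the response count fixed, a larger n can only raise it. The null hypothesis is not rejected under either definition.

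**The case against.** Several points on the other side are sound. The affected group is close to empty, because exclusion requires never once taking the full starting dose. SAP 10.1.1 reports the number treated and the size of each population, and lists the reason for each exclusion, so a reader could rebuild the full denominator. Protocol 11.5.1 leaves statistical detail to the SAP, and the protocol does not define what receiving study drug means. Enrolment has been halted, the interim homogeneity assessment was not done, and efficacy is reported by cohort and pooled (SAP 10 and 10.2), so no decision turns on one or two subjects.

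These points settle the priority. They do not remove the inconsistency: listing an exclusion does not reverse it, and a clarification that gives one phrase opposite meanings in 7.2 and 7.5 is more than added detail.

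A reader might infer three stronger things that the documents do not support.

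- *That the rule can only raise ORR and DCR, because everyone it removes is an early failure.* The rule asks whether a full dose was ever taken, not whether the subject stopped early. A persistently under-dosed subject could stay on drug and respond or have stable disease; excluding that subject would lower the rate. Upward is the likely direction, not a certain one.
- *That the effect can be shown by shrinking 63 to 62 using the four local responses.* Those are investigator-read and unconfirmed, and the 63 are probably inside the SAP's ITT already.
- *That type I error is materially inflated.* At the planned pooled size of 113 (27 + 86), the critical count stays at 24 responses with up to four exclusions and falls to 23 only at five. Nothing in the documents suggests that many, and enrolment was halted after the review of 63 evaluable subjects.

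**Conclusion.** The discrepancy is real and can be read directly from the two documents. SAP 7.2 narrows the protocol's primary efficacy population, contrary to the SAP's own statement of compliance, and a treated subject who never took one full dose drops out of ITT, mITT and PP. The exclusion would tend to raise ORR slightly.

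On the assumed zero to two subjects, the pooled rate in the illustration differs by at most 0.14 percentage points and the conclusion against 15% is unaffected. That size rests on three assumptions: the count of affected subjects, which the documents do not give; that the 63 evaluable subjects already meet the SAP's ITT rule; and that central unconfirmed responses are an acceptable stand-in for the confirmed primary endpoint. The definitional point depends on none of them. Low priority.

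**What to change.** Amend the operational sentence in SAP 7.2 so that receiving study drug means any full or partial dose, in the same words as SAP 7.5 and in line with Protocol 11.3. ITT, the Safety set and the treated count in the disposition table then coincide, and mITT and PP inherit the correction without further edits.

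If the sponsor prefers to keep the threshold, the SAP should state it as a departure from the protocol, justify it, name the data source that establishes a full dose, and report ORR on the Safety set as well.

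The first option costs one sentence and a matching change to the ITT flag. It needs no new data and should be made before the database lock for the main analysis.

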7.3 Modified Intent-to-Treat Population (mITT)

The modified intent-to-treat (mITT) population consists of all subjects in the ITT population whose gene fusion/rearrangement has been confirmed by central testing.

A patient has gene fusion/rearrangement confirmed by central testing if the patient appears in the Caris central lab external dataset and has a result of gene fusion/rearrangement being present. Subjects will be analyzed according to their assigned cohort.

7.4 Per Protocol Population (PP)

The per protocol (PP) population consists of all subjects in the ITT population who have undergone radiographic assessment at baseline (i.e., tumor assessment screening visit), received at least one dose of study drug, had both baseline and post-baseline disease and had no critical protocol deviation that may have an impact on efficacy endpoints.

Having radiographic assessment at baseline and baseline disease is considered met if inclusion criterion 7 (having measurable disease according to RECIST 1.1 at baseline) is Yes.

Having post-baseline disease is clarified as requiring at least 1 post-baseline disease assessment.

Critical protocol deviations that may have an impact on efficacy endpoints are defined as (also see Section 13.6):

- Violation of any inclusion/exclusion criteria at entry.
- Actual cumulative dose below 75% of planned cumulative dose from date of first dose to date of end of cycle 4 or date of treatment discontinuation, whichever occurs first.
- Subject data indicate a major protocol deviation other than the criteria defined above, that potentially affects efficacy assessment and is identified prior to database lock.

7.5 Safety Population (SAF)

The Safety population consists of all subjects who received study drug.

Receiving study drug is considered to have taken at least 1 full dose or partial dose of study drug.

7.6 PK Population (PKP)

The PK population (PKP) will include subjects who received one or more doses of Debio 1347 and have at least one PK concentration result available.

Receiving one or more doses of Debio 1347 is considered to have taken at least 1 full dose of study drug.

7.7 C-QT Population (CQP)

The C-QT population (CQP) will include subjects in PK population who has at least one matching ECG evaluation and PK sampling.

The C-QT population will be used for exposure-response (C-QTcF) analysis. However, whether the exposure-response analysis is performed will depend on the outcome of safety and efficacy analyses and data availability.

A matching ECG evaluation and PK sampling pair is defined as follows: measurements for which the elapsed time between the two is within a time window of +/- 30 minutes (for pre-dose and 7h post-dosing time points) and +/- 20 minutes (for 1h and 3h post-dosing time points). Pairs for which the elapsed time between the two assessments is outside these windows will be excluded from the analysis. If more than 30% of pairs are excluded at 1h and 3h time points because of deviations from the protocol-defined window for ECG measurement (within 20 min of PK samplings), the analysis will be repeated using a time window of +/-30 min for 1h and 3h post-dose time points.

8 DATA HANDLING

8.1 Missing Data

In subject listings, incomplete dates will be presented as collected in the electronic case report form (eCRF). In order to identify whether an AE is treatment-emergent or whether a medication is prior or concomitant, partial dates missing the day, or both the day and month of the year will be considered as outlined below.

8.1.1 Adverse Event

When the day of onset of an AE is missing:

- If month and year of onset of an AE is the same as the month and year of date of first administration of the study drug:
 - If AE end date contains a full date and end date is earlier than study treatment start date, then the missing onset day is entered as the 1st of the month.
 - Otherwise, the missing onset day is entered as the day of date of first administration of the study drug.
- If month and year of onset of an AE is not the same as the month and year of date of first administration of the study drug, the missing onset day is entered as 1st of the month.

When the day and month of onset of an AE are missing:

- If year of onset of an AE is the same as the year of date of first administration of the study drug:

- If AE end date contains a full date and end date is earlier than study treatment start date, then the missing onset day and month are imputed as January 1st.
- Otherwise, the missing onset day and month are imputed as the day and month of date of first administration of the study drug
- If year of onset of an AE is not the same as the year of date of first administration of the study drug, the missing onset day and month are imputed as January 1st.

If AE onset date is completely missing:

- If AE end date is on or after the date of first administration of the study drug, then onset date is set to date of first administration of the study drug.
- If AE end date is prior to the date of first administration of the study drug, then onset date is not imputed, and AE is not considered as treatment-emergent.

If AE end date is prior to the date of first administration of the study drug, then onset date is not imputed, and AE is not considered as treatment-emergent.

If AE end day is missing, then end day will be imputed as last day of the month, or end date of the on-treatment period, whichever is earlier

If AE end day or month are missing, then end day will be imputed as last day of the month and end month will be imputed as December, or end date of the on-treatment period, whichever is earlier.

If AE end date is completely missing, then imputed as end date of the on-treatment period.

8.1.2 Concomitant Medications

End date: Missing day will be imputed as the last day of the month, and missing month will be imputed as December.

Start date: Missing day will be imputed as the first day of the month, and missing month will be imputed by January. If the start date is completely missing, then:

- If the end date is prior to the date of first administration of the study drug, then the medication is considered as prior
- If the end date is prior to or on the date of last administration of the study drug, then the medication is considered as prior and concomitant
- If the end date is completely missing or after the date of last administration of the study drug, then the medication is considered as prior, concomitant and post.

8.2 Coding

Medical history and AEs will be coded using Medical Dictionary for Regulatory Activities (MedDRA) v23.0 (March 2020). Prior and concomitant medications will be coded using the last available World Health Organization Drug Dictionary (WHO-DD) Global B3 March 2020.

8.3 Handling of Values Below (or Above) a Threshold

For statistical and graphical summaries of the safety laboratory tests, values below or above the limit of detection (e.g. '< 3' or '>500') are substituted with the lower/upper limit of detection (e.g. '< 3' is substituted by '3', '> 500' is substituted by '500'). In data listings, the values will be shown as collected, e.g. including the < or > sign.

In the PK analysis, Debio 1347 plasma concentrations below the limit of quantification (BLOQ) will be set to ½ LOQ for calculation of all summary statistics.

Handling of BLOQ values for deriving PK parameters will be described in the dedicated Data Analysis Plan for population PK analysis (cf. study Debio 1347-507).

8.4 Handling of Unscheduled Assessments or Retests

In case of pre-dose retests, the latest value will be used in the analysis. The post-dose retests and the unscheduled assessments will not be used in the summary statistics but will be used in the derivation of endpoints that are not related to a specific timepoint (i.e. worst-case assessment, BOR, time to event endpoints, etc.). They will also be displayed in listings.

9 GENERAL STATISTICAL CONSIDERATIONS

9.1 General Conventions

The statistical analysis described below corresponds to analysis planned for the study. Any deviation from the planned analysis will be documented in clinical study report.

Continuous data will be presented in the form of descriptive statistics, as the number of observations, mean, standard deviation, minimum, 25th percentile (Q1), median, 75th percentile (Q3) and maximum.

Categorical data, including ordinal data, will be presented using contingency tables with absolute and relative frequencies. Missing will be considered as a category and included in the calculation of percentages, unless otherwise stated.

For time-to-event endpoints, Kaplan Meier (K-M) estimates will be provided and include number and percentage of events/censored, 25th (Q1), median and 75th (Q3) survival time and associated 95% confidence interval (CI, if applicable), survival rate and 95% CI at pre-specified time points. For the CIs, these will be Brookmeyer-Crowley for the survival time quartiles and Greenwood for the survival rate.

For PK parameters and concentrations, summary statistics in the tabulation will include number of non-missing value, number below the LOQ, mean, standard deviation, Q1, Q3, 90% CI of the arithmetic mean, coefficient of variation (CV%), median, minimum, maximum, geometric mean, 90% CI of the geometric mean, geometric standard deviation [calculated as: $\text{geo standard deviation} = \exp(\text{SDlog})$] and geometric CV% [calculated as: $\text{geo CV\%} = \text{SQRT}(\exp(\text{SDlog}^2) - 1) * 100\%$; where SDlog is the standard deviation of the log-transformed values].

The minimum and maximum will be reported to the same number of decimal places as the raw data recorded in the database. The mean, median, confidence intervals, Q1 and Q3 will be reported to one more decimal place than the raw data recorded in the database. The standard deviation will be reported to two more decimal places than the raw data recorded in the database. Percentages will be reported with one decimal place. The CV% is reported as a percentage with 1 decimal place.

Baseline measurement is the latest value collected prior to the administration of study drug.

All data analyses will be performed using SAS® statistical software version 9.4 or higher, R software version 3.3 or higher and NONMEM®.

9.2 Dates, Times and Days

Study day is defined as:

- (Date of event) – (Date of first dose of study drug) + 1, if the event is on or after the date of first dose;
- (Date of event) – (Date of first dose of study drug), if the event is before the date of first dose.

9.3 Timing of Analyses

The timing of the first IDMC meeting was as planned:

- The first IDMC meeting will take place after 15 subjects have either been on treatment for at least 8 weeks or discontinued the study treatment.

The timing of the second IDMC meeting was planned to be conducted at same time as the interim analysis:

- The second IDMC meeting will be convened to review the Interim Analysis results. An interim analysis will be conducted at end of Stage 1 to assess ORR homogeneity across baskets as well as futility. A minimum of 4 subjects per cohort and a maximum of 13 subjects per cohort will be required for the end of Stage 1 analysis (see Section 10.8 for full details of the planned interim analysis).
- However, the second IDMC meeting took place with 63 evaluable subjects (30, 4, and 29 in cohorts 1, 2 and 3, respectively).

The timing of the main analysis will be modified by Protocol Amendment 2 as follows:

- The main analysis will be conducted with all the safety and efficacy data after the last subject has consented to Protocol Amendment N° 2. The data from this analysis will be used to write an abbreviated clinical study report (CSR).

The final descriptive analysis will be conducted as planned:

- A final descriptive analysis focused on safety will be conducted after the last subject has completed the EOS visit.
- As the study ended earlier than expected, it is decided to conduct the main analysis and the final descriptive analysis at the same time after the last subject has completed the EOS visit.

